## 10. APPENDICES

### 10.1 TIME SCHEDULE FOR PHARMACOKINETIC (PK) AND ADA BLOOD SAMPLING AND AQUEOUS SAMPLING

Table 10.1: 1 Time schedule for PK and [REDACTED] sampling (SRD part)

Course	Visit	Day/ Week	Planned Time	Planned Time [h]	PK BI 764524	[REDACTED]
1	V2	1	Before drug administration of BI 764524*	-0:30	X	X
	V2	1	Drug administration	0:00		
	V2	1	30 min after drug administration*	00:30	X	
	V3	4 (+/- 1 day)	3 days after drug administration	72:00	X	
	V4	8 (+/- 2 day)/ Week 1	1 week after drug administration	168:00	X	
	V5	15 (+/- 2 day)/ Week 2	2 weeks after drug administration	336:00	X	X
	V6	29 (+/- 3 day)/ Week 4	4 weeks after drug administration	672:00	X	X
	V7	57 (+/- 7 day)/ Week 8	8 weeks after drug administration	1344:00	X	
EOS	V8	99 (+/- 7 day)/ Week 14	12 weeks after drug administration	2016:00	X	X**

\* A time window of +/-15 min for sample drawing is allowed.

\*\*If there is [REDACTED] occurrence a further follow-up will be conducted.

Table 10.1: 2 Time schedule for PK and [REDACTED] blood sampling (MD part)

Course	Visit	Day/ Week	Planned Time	Planned Time [h]	PK BI 764524	[REDACTED]
1	V2	1*	Before drug administration of BI 764524	-0:30	X	X
	V2	1	First Drug administration	0:00		
	V3	29 (+/- 3 day)*/ Week 4	4 weeks after first drug administration; predose to 2 nd drug administration	671:30	X	X
	V3	29(+/- 3 day)/ Week 4	Second Drug administration	672:00		
	V4	57 (+/- 3 day)*/ Week 8	8 weeks after first drug administration; predose to 3 rd drug administration	1343:30	X	
	V4	57 (+/- 3 day)/ Week 8	Third Drug administration	1344:00		
Follow Up Period	V5	85 (+/- 7 day)/ Week 12	12 weeks after first drug administration	2016:00	X	X**
Follow Up Period	V6	113 (+/- 7 day)/ Week 16	16 weeks after first drug administration	2688:00	X	
Follow Up Period	V7	155 (+/- 7 day)/ Week 22	22 weeks after first drug administration	3360:00	X	

\*A time window of 30 mins to 2 hrs before dosing is allowed for sample drawing. PK and [REDACTED] samples must be taken before next drug administration; no window afterwards.

\*\*If there is [REDACTED] occurrence a further follow-up will be conducted.

Table 10.1: 3 Time schedule for optional Aqueous sampling (MD part)

Trial Periods	Visit	Day	Time Point	Optional Aqueous sampling
Treatment	2	1	Just before drug administration	X*
	3	29 (±3)		
	4	57 (±3)	Just before drug administration	X*
Follow-up	5	85 (±7)		
Follow-up	6	113 (±7)	Any time during the visit	X*
EOS	7	155 (±7)	Any time during the visit	X*

\* Optional aqueous samples are collected immediately before drug administration at Visits 2 and 4. At visits 6 and 7, when no drug is administered, the aqueous samples can be collected at any time during the visit.

## 10.2 STATISTICAL APPENDIX

A BLRM with overdose control will be used to guide dose escalation in this study. The BLRM is introduced in Section 7.1, which also specifies the prior for the model. After patients in each cohort have completed the evaluation period of 7 days, the prior distribution will be updated through Gibbs sampling procedures with the accumulated DLE data from the evaluation period. Posterior probabilities for the rate of DLEs will be summarized from the BLRM. Selection of the next dose will be based on these probabilities as well as on other safety and laboratory data.

The purpose of this statistical appendix is to present performance metrics (operating characteristics) that illustrate the precision of the design in estimating the MFD (see Section 3.1) under various dose-toxicity relationships through computer simulation. These results are summarized in Table 10.2: 3. In addition, recommendations of the next dose level by the BLRM with overdose control principle are provided under various hypothetical outcome scenarios in early cohorts, to show how it facilitates on-study dose-escalation decisions (see Table 10.2: 1). For simplicity reasons, a cohort size of 3 patients who are all evaluable is assumed.

### Hypothetical data scenarios

Hypothetical data scenarios are shown in Table 10.2: 1. These scenarios reflect potential on-study data constellations and related escalation as allowed by the model and the planned dose groups. It is assumed that each cohort has exactly three patients who are all evaluable. For each scenario, the probability of overdose for the current dose, as well as the next potential dose and related probabilities of target dosing and over-dosing are shown (probability of over-dosing: P(OD), probability of target dosing: P(TD)).

For example, scenario 1 represents the case that no DLE is observed in 3 patients at the starting dose of [REDACTED]. In this case, the next planned dose permitted by the model and the 200% escalation rule is [REDACTED]. In contrast, scenario 2 assumes that there is one DLE observed in the first dose group. This would mean over toxicity from the beginning, and the recommendation would be to stop the trial.

In scenario 3, there is no DLE after the first 2 dose groups, which would allow the trial to continue to the next dose level. If no further DLE occurs in the trial (scenario 6c), dose escalation would proceed to the [REDACTED] dose, with an additional cohort at that dose level at the end, i.e. overall 12 patients.

In scenario 4, the first DLE occurs in dose group [REDACTED]. Then the recommendation would be to treat an additional cohort of 3 patients at the same dose level. If no new DLE occurs then, scenario 4b shows that the next recommended dose level would be [REDACTED]. Thus, the [REDACTED] dose would be declared as MFD and the trial would stop (after 9 patients).

However, if (after repeating dose group [REDACTED] according to the recommendation from scenario 4) there was another DLE in the second cohort for dose group [REDACTED] (as in scenario 5), then the recommendation would be to go back to dose [REDACTED]. If there was no further DLE then (scenario 5b), the recommendation would be to go to next dose [REDACTED]. If there was no DLE in the third cohort of [REDACTED] (scenario 5c), then the trial would stop after 15 patients and declaring [REDACTED] as the MFD.

Scenario 6b shows the case where the first DLE occurs in the [REDACTED] dose group. Then an additional cohort of 3 patients would have to be treated at [REDACTED] dose group. If these 3 patients have no further DLE, the next recommended dose would be [REDACTED]. If this second cohort of 3 patients in the [REDACTED] group have no DLE (scenario 6c) the next recommended dose would be [REDACTED]. If this second cohort of 3 patients in the [REDACTED] group have no DLE (scenario 6c) the next recommended dose would be [REDACTED]. Thus, the [REDACTED] dose would be declared as MFD and the trial would stop (after 15 patients)

Table 10.2: 1 Hypothetical data scenarios

Scenario	Dose (mg)	# Pat.	# DLE	Current Dose: P(OD)	Next recomm. dose	Next dose:	
						P(TD)	P(OD)
1	[REDACTED]	3	0	0.025	1	0.945	0.055
2	[REDACTED]	3	1	0.345	N/A	N/A	N/A
3	[REDACTED]	3	0	0.016	2.5	0.874	0.126
		3	0				
4	[REDACTED]	3	0	0.209	1	0.791	0.209
		3	1				
4b	[REDACTED]	3	0	0.091	1	0.909	0.091
		6	1				

Table 10.2: 1 Hypothetical data scenarios (continued)

Scenario	Dose (mg)	# Pat.	# DLE	Current Dose: P(OD)	Next recomm. dose	Next dose:	
						P(TD)	P(OD)
5		3	0	0.329	0.5	0.867	0.133
		6	2				
5b		6	0	0.022	1	0.884	0.116
		6	2				
5c		6	0	0.884	1	0.884	0.116
		9	2				
6		3	0	0.036	2.5	0.964	0.036
		3	0				
		3	0				
6a		3	0	0.013	2.5	0.987	0.013
		3	0				
		6	0				
6b		3	0	0.285	1.0	0.969	0.031
		3	0				
		3	1				
6c		3	0	0.015	2.5	0.772	0.228
		6	0				
		3	1				
6d		3	0	0.103	2.5	0.897	0.103
		6	0				
		6	1				
6e		3	0	0.098	1	0.902	0.098
		6	1				
		3	1				

### Operating characteristics

Operating characteristics are a way to assess the long-run behavior of a model by illustrating the precision of the design in estimating the MFD. Under an assumed true dose-toxicity curve, metrics such as the probability of recommending a dose with true DLE rate in the target interval can be approximated via simulation. Table [10.2: 2](#) describes 6 assumed true dose-toxicity scenarios which were used to assess the operating characteristics of the model. These scenarios reflect a wide range of possible cases as follows:

- Scenario 1: aligned with prior medians
- Scenario 2: aligned with prior means
- Scenario 3: high-toxicity scenario

- Scenario 4: low-toxicity scenario
- Scenario 5: non-logistic dose-toxicity scenario
- Scenario 6: low-toxicity followed by high-toxicity

Table 10.2: 2 Assumed true dose-toxicity scenarios

Scenario		Dose (mg)			
		■	■	■	■
1: Prior Med	P(DLE)	0.014	0.024	0.054	0.112
2: Prior Mean		0.086	0.106	0.153	0.224
3: High Tox		0.150	0.200	0.280	0.350
4: Low Tox		0.001	0.005	0.010	0.100
5: Non-Logistic		0.050	0.010	0.200	0.500
6: Low-High		0.010	0.050	0.400	0.600

For each of these scenarios, 1000 trials were simulated. Each cohort consisted of 3 patients and dose escalation complied with the following rule:

*Escalate to the maximum dose which satisfies the overdose criterion and is  $\leq 500\%$  increase from the current dose.*

The MFD was considered reached if at least 6 patients have been evaluated at a dose level which is the model's recommendation for the next dose cohort. The maximum allowed patient number for each trial was chosen as 24.

It was then assessed how often a dose was declared as MFD with true DLE rate in the targeted or in the overdosing range. Furthermore, the average, minimum and maximum number of patients per trial and the average number of DLEs per trial are reported. Results are shown in Table [10.2: 3](#).

Table 10.2: 3 Simulated operating characteristics

Scenario	Max. allowed # Patients	% of trials declaring a MFD with true DLE rate in		% of stopped trials*	# Patients	# DLEs
		[██████] target dosing	[██████] overdosing		Mean (Min-Max)	Mean (Min-Max)
1	15	94.1	0.0	5.9	11.8 (3-15)	0.39 (0-3)
2	15	65.4	0.0	34.6	9.1 (3-15)	1.10 (0-4)
3	15	23.8	13.6	62.6	8.5 (3-15)	1.88 (0-6)
4	15	100	0	0	9.2 (9-15)	0.06 (0-1)
5	15	67.9	0	32.1	10.7 (3-15)	1.16 (0-4)
6	15	47.9	20.3	31.8	13.1 (3-15)	2.01 (0-5)

\* The stopped trials include early stopped trials (stopped due to too much toxicity), as well as trials that stopped because the maximum allowed patient number was reached before an MFD was found.

In scenario 1, which reflects the case that the true dose-toxicity is aligned with prior medians, 94.1% of the simulated trials declared a dose as MFD with true DLE rate in the targeted toxicity range. Note that 5.9% of the simulated trials stopped either because there was no MFD determined after 15 patients had been observed (1.4 %) or because of too high toxicity for the planned doses (4.5 %). This latter is mostly due to the cases that 1 DLE is observed out of 3 patients at the starting dose of [██████]. In reality, this situation would rarely happen as the safety profile of starting dose is expected to be good.

In scenario 2, the assumed dose toxicities are higher than in scenario 1. This results in a higher percentage of early stopped trials (about 34.6 %). In this case, about 65.4 % of the trials would end with an estimated MFD within the targeted toxicity range, and 27.7 % in the overdosing range.

In Scenario 3 (high-toxicity scenario), only 23.8% of the trials declared a dose as MFD with true DLE rate in the targeted toxicity range. In 13.6% of the trials, the estimated MFD was in the overdosing range. Scenario 4 (low-toxicity scenario) shows the best results, i.e. the lowest number of stopped trials and a high number of trials with estimated MFD in the target range, as would be expected.

Scenarios 5 and 6 showed reasonable operating characteristics, given the quite large deviations of the assumed true dose-toxicity curve from the assumptions underlying the BLRM.

The mean patient numbers ranged from 8.5 patients (Scenario 3) to 13.1 patients (Scenario 6), and the maximum number of patients was 18. Therefore, the patient numbers are as expected and increase when moving away from the high-toxicity scenario.

Overall, by reviewing the metrics presented in table [10.2: 3](#), it can be seen that the model is generally conservative due to the overdose control criteria. In all scenarios, except for the

high-toxicity case (scenario 3) the probabilities of recommending a dose with true DLE rate being at least 25%,  $P(\text{DLE} \geq 25\%)$ , as MFD are much smaller than the probabilities of recommending a dose with true  $P(\text{DLE}) < 25\%$  as MFD.

R version 3.5.1 was used for data scenarios and simulations.

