##### SRD part:

In the SRD part, the starting dose is [REDACTED]. The other provisional dose level is [REDACTED], and the maximum planned dose is [REDACTED]. For each cohort, a single patient will be dosed on day 1, and the dosing investigator, coordinating investigator and 2 representatives of the sponsor who are involved in the trial will carefully evaluate all available systemic (i.e. physical examinations, safety lab parameters, ECG and AEs) and ophthalmologic (i.e. as defined in Section 5.2.1) safety data until day 4. If this patient neither has experienced an ophthalmologic nor a systemic serious adverse event, the remaining 2 patients will be dosed. Written minutes of this assessment are being distributed to all investigators participating in this trial.

For any dose-escalation cohort, at least 3 evaluable patients will be required. Each cohort will consist of newly enrolled patients.

A Safety Monitoring Committee (SMC, see Section 8.7) will decide on the next dose level to be investigated and on the size of the next cohort based on occurrence of DLEs and on additional information (systemic PK and patient profiles). Systemic PK data from preceding cohorts (not from the ongoing cohort) will be available for evaluation. First SMC meeting will take decision based on safety data only. Refer to figure 3.1:1 (SRD) and figure 3.1:2 (MD) for a schematic representation of the dose escalation.

A Bayesian logistic regression model (BLRM), based on a weekly informative prior distribution, and employing the escalation with overdose control (EWOC) principle (see Section 7) will be used for guiding the dose escalation [R13-4803]. After all patients in a cohort have either experienced a DLE or have been observed for at least the 7 days evaluation period without experiencing a DLE (I.e. 7 days after drug administration, until visit 4, will be evaluated per patient), the BLRM will be updated with the newly accumulated data. The overdose risk will then be calculated for each dose, and escalation will be permitted to all planned doses which fulfil the EWOC criterion and the respective escalation rule.

The BLRM provides estimates for the probability of observing a DLE for each planned dose. Dose escalation will be permitted to the next planned dose which fulfils the EWOC criterion. Note that this may also result in repeating the current dose level, or in going down to a lower dose level again.

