If DLEs are observed in the first two consecutive patients of a previously untested dose level, subsequent enrolment to that cohort will be stopped.

The maximum feasible dose (MFD) is considered as reached if at least 6 patients have been evaluated at a dose level which is the model's recommendation for the next dose cohort. Note the MFD will likely be the highest feasible dose, [REDACTED], rather than the highest tolerable dose in strict sense. The MD part of the study would only start if the highest dose ([REDACTED]) is tolerated.

- After the DLE period (7 days after drug administration) is over for the last patient in the SRD part, all available trial data will be analyzed and a decision is made whether to proceed to the MD part or not. Before starting the MD part, regulatory authorities and institutional review boards (IRBs) / independent ethics committees (IECs) will be informed of the internal results of the SRD part.

[figure not shown]

Figure 3.1: 1 Schematic representation of the dose escalation process in the SRD part of the trial

MD part:

The MD part will consist of one dose cohort (N=20 on dose + 10 sham injection). The highest dose [REDACTED] if established as safe and tolerable during the SRD part will be used in the MD part after the SRD part has been completed. Patients that had received a dose in the SRD part of the trial will not be included. Patients will be randomized to receive either active treatment or sham injection.

In the MD cohort, patients will receive three consecutive doses/sham injection over a 3-month period (dosing every 4 weeks). The SMC will meet regularly to review the safety data.

In all patients included in the MD part of the trial, safety and early biological response will be studied up to 98 days after the last injection.

[figure not shown]

Figure 3.1: 2                      Schematic representation of the dosing in the MD part of the trial

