#### SRD part

The dose escalation will be guided by a Bayesian 2-parameter logistic regression model with overdose control [R13-4803, R13-4806]. For a given dose, the EWOC criterion is that there should be less than 25% risk that the true ocular DLE rate is above 0.25.

The model is given as follows:

$$\text{logit}(\pi_d) = \log(\alpha) + \beta \cdot \log(d/d^*),$$

where  $\text{logit}(\pi) = \log(\pi/(1-\pi))$ ,  $\pi_d$  represents the probability of having a DLE in the evaluation period at dose  $d$ ,  $d^* = \blacksquare$  is the reference dose, allowing for the interpretation of  $\alpha$  as the odds of a DLE at dose  $d^*$ , and  $\theta = (\log(\alpha), \log(\beta))$  with  $\alpha, \beta > 0$  is the parameter vector of the model.

The estimated probability of a DLE at each dose level from the model will be summarized using the following intervals:

Target toxicity: [0.00, 0.25)

Over toxicity: [0.25, 1.00]

The BLRM-recommended dose for the next cohort is the dose level with the highest posterior probability of the DLE rate falling in the target interval [0.00, 0.25) among the doses fulfilling EWOC. Thus, it should be unlikely (< 25% posterior probability) that the DLE rate at that dose will exceed 0.25. However, the allowed dose increment will always be the next higher pre-planned dose. However, the maximum allowable dose increment for the subsequent cohort will be no more than 250% from the previous dose. Dose escalation will continue up to the  $\blacksquare$  dose as long as the EWOC criterion for the next dose level is fulfilled. At the final dose, at least 6 treated patients are required. However, the SMC may decide to include additional number of patients at this dose level.

Since a Bayesian approach is applied, a prior distribution  $f(\theta)$  for the unknown parameter vector  $\theta$  needs to be specified. This prior distribution will be specified as a mixture of three multivariate normal distributions, i.e.

$$f(\theta) = a_1 f_1(\theta) + a_2 f_2(\theta) + a_3 f_3(\theta)$$

with  $a_i$ ,  $i = 1, 2, 3$  the prior mixture weights ( $a_1 + a_2 + a_3 = 1$ ), and  $f_i(\theta) = \text{MVN}(\mu_i, \Sigma_i)$ , the multivariate normal distribution of the  $i$ -th component with mean vector  $\mu_i$  and covariance matrix  $\Sigma_i$ , where

$$\Sigma_i = \begin{pmatrix} \sigma^2_{i,11} & \sigma_{i,11}\sigma_{i,22}\rho_i \\ \sigma_{i,11}\sigma_{i,22}\rho_i & \sigma^2_{i,22} \end{pmatrix}.$$

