A summary of the prior distribution is provided in Table [7.1: 1](#). Additionally, the prior probabilities of DLEs at different doses, as well as the corresponding probability of targeted and overdosing, are shown in Table [7.1: 2](#). Graphically, the prior medians with accompanying 95% credible intervals are shown in Figure [7.1: 1](#). As can be seen from both Table [7.1: 2](#) and Figure [7.1: 1](#), the prior medians of the DLE probabilities are in line with the prior medians derived from the weakly informative prior, and the uncertainty around the medians is large, showing the low amount of information this prior provides. This is also supported by the prior sample size, i.e. the information contained in the prior. This is approximately equal to 1.7 patients. A detailed evaluation of the model using hypothetical data scenarios and operating characteristics is provided in Appendix [10.2](#).

Table 7.1: 1 Summary of prior distribution

Prior Component	Mixture Weight	Mean Vector	SD Vector
1: Weakly inf.	0.900	-2.005 0.0516	2.00 1.00
2: High Tox.	0.050	-0.255 -0.191	2.00 1.00
3: Low Tox.	0.050	-4.516 -0.835	5.00 0.01

Table 7.1: 2 Prior probabilities of DLEs at selected doses

Dose	Probability of true DLE rate		mean	sd	Quantiles		
	(0-0.25]	[0.25-1]			2.50%	50%	97.50%
0.5	0.883	0.117	0.091	0.170	0	0.013	0.703
1	0.836	0.164	0.121	0.201	0	0.025	0.775
2.5	0.714	0.286	0.202	0.245	0.001	0.092	0.880

[figure not shown]

Figure 7.1: 1 Prior medians and 95% credible intervals

The prior may be updated once the trial has started in case new data that can be used will be available. Only patients for which the occurrence of DLEs within the evaluation period can be evaluated will be considered. The prior that is used for each BLRM analysis for the SMC meetings will be documented in the SMC minutes, the prior used for the final analysis will be documented in the TSAP.

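### The operating characteristics in Protocol Appendix 10.2 were not simulated under the planned single-rising-dose rules, and scenario 4's mean of 9.2 patients cannot occur under them

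*Protocol*

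**What the plan says.** **Planned escalation.** Protocol Section 3.1: "Dose escalation will be permitted to the next planned dose which fulfils the EWOC criterion". Section 7.1 is stricter: "the allowed dose increment will always be the next higher pre-planned dose", and the increment "will be no more than 250% from the previous dose". Section 7.1 also states: "At the final dose, at least 6 treated patients are required". The worked examples in Appendix 10.2 cite a different cap, "the next planned dose permitted by the model and the 200% escalation rule", and give 12 patients for a trial with no DLE.

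**Maximum feasible dose (MFD).** Section 3.1: "The maximum feasible dose (MFD) is considered as reached if at least 6 patients have been evaluated at a dose level" that the model recommends for the next cohort.

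**Simulated escalation.** Appendix 10.2, Operating characteristics: "Escalate to the maximum dose which satisfies the overdose criterion", provided the increase is at most 500%. Cohorts are of 3, with 1000 trials per scenario. The text sets the patient cap at 24; Table 10.2:3 shows 15.

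**Use of the results.** Section 7.7 cites the simulation for about 15 evaluable patients. Appendix 10.2 concludes from Table 10.2:3 that the model is generally conservative.

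**The concern.** Operating characteristics inform a reader only if they come from the design that will be run. From 0.5 to 2.5 mg is (2.5 − 0.5)/0.5 = +400%, which the simulated rule allows and Section 7.1 forbids. If the simulation skipped the middle dose, its patient numbers, selection percentages and DLE counts describe another trial, and the justification in Section 7.7 cannot be reproduced from the planned rules.

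Several figures in the same appendix also contradict each other, which suggests that parts of it predate the removal of the fourth dose.

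**Working it through.** **1. Bound for scenario 4, without any model.** The Table 10.2:2 rates at the first three doses are 0.001, 0.005 and 0.010. A DLE-free trial under the plan uses 3 + 3 + 6 = 12 patients.

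P(no DLE in 12) = 0.999³ × 0.995³ × 0.99⁶ = 0.925.

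Even if every other trial stopped after 3 patients, mean N ≥ 0.925 × 12 + 0.075 × 3 = 11.3. With the table's own minimum of 9 it is 0.925 × 12 + 0.075 × 9 = 11.8. The printed mean is 9.2.

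**2. Reproducing the model.** Inputs are the three-component prior and the overdose criterion of Section 7.1 (posterior P(DLE rate above 0.25) below 0.25), doses 0.5, 1 and 2.5 mg from Table 7.1:2, cohorts of 3 and a cap of 15. The reference dose is redacted; I assume 3 mg. P(OD) is the probability of overdosing.

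| Check | Recomputed | Printed |
|---|---|---|
| Prior P(OD) at 0.5 / 1 / 2.5 mg | 0.117 / 0.162 / 0.290 | 0.117 / 0.164 / 0.286 |
| After 0/3 at 0.5 mg: P(OD) at 0.5 / 1 mg | 0.025 / 0.055 | 0.025 / 0.055 |
| After 1/3 at 0.5 mg: P(OD) at 0.5 mg | 0.344 | 0.345 |

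Rows 6b and 6c of Table 10.2:1 hold only for a reference dose of about 2.9 to 3.4 mg, so the assumption is tightly constrained.

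**3. Does the simulated rule skip?** After 0/3 at 0.5 mg, P(OD) at 2.5 mg is about 0.18, below 0.25. It therefore goes straight to 2.5 mg, and a DLE-free trial ends at 3 + 6 = 9 patients.

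**4. Both rules, all outcome paths enumerated.** MFD is declared only at the current dose.

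| Scenario | Printed mean N | Skipping | Next dose only | Printed target/over/stopped % | Next dose only % |
|---|---|---|---|---|---|
| 1 | 11.8 | 9.62 | 11.83 | 94.1/0/5.9 | 93.8/0/6.2 |
| 2 | 9.1 | 9.15 | 9.88 | 65.4/0/34.6 | 66.6/0/33.4 |
| 3 | 8.5 | 8.41 | 8.22 | 23.8/13.6/62.6 | 31.3/12.1/56.6 |
| 4 | 9.2 | 9.16 | 12.02 | 100/0/0 | 99.6/0/0.4 |
| 5 | 10.7 | 10.76 | 11.71 | 67.9/0/32.1 | 70.6/0/29.4 |
| 6 | 13.1 | 13.09 | 12.55 | 47.9/20.3/31.8 | 53.2/18.3/28.5 |

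In Monte Carlo standard errors for 1000 trials, the printed means for scenarios 2, 4, 5 and 6 lie 5.7, 112, 8.3 and 6.6 from next-dose escalation and at most 1.2 from skipping. Scenario 1 is the reverse: 0.4 from next-dose, 28 from skipping.

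Scenario 3 fits neither rule at its tabulated rates. Next-dose target selection is 5.1 standard errors off, and skipping gives 21.2% overdosing, 5.8 off. Skipping with 0.350 (the fourth-column rate) at the third dose gives 23.1/14.1/62.9 and mean N 8.6, close to the printed row.

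**5. MFD wording.** Read literally, any recommended dose with 6 patients qualifies. Examples 5b and 5c continue to 15 patients, which means only the current dose counts. Under next-dose escalation in scenario 6, the literal reading gives 77.9% target selection against 53.2%.

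**6. Other figures in Appendix 10.2.**
- Table 10.2:2 keeps four dose columns for three doses. Its prior median and mean at the third dose are 0.054 and 0.153; Table 7.1:2 has 0.092 and 0.202. With the current values and next-dose escalation, target selection is 91.2% (mean N 12.1) in scenario 1 and 62.3% (9.8) in scenario 2.
- The text gives 27.7% overdosing in scenario 2. All its rates are below 0.25, the table says 0.0, and 65.4 + 34.6 is already 100.
- The text has a cap of 24 and a maximum of 18 patients; the table has 15 for both.
- Table 10.2:1, row 5b prints row 5c's next-dose values: P(OD) should be about 0.22, not 0.116. Row 5c's current-dose P(OD) of 0.884 is its target probability; it should be about 0.116.

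**The case against.** The strongest reply is that this comes too late to matter. Protocol Section 1.2 reports 12 patients treated with no DLE, SAP Section 6.1 confirms 12 enrolled, and the planned SRD analysis is counts and percentages, into which Table 10.2:3 does not enter. That stands and limits the importance. It does not make the documented justification right.

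Section 3.1 also has a looser sentence allowing all planned doses that meet the criterion. But that sentence defers to the respective escalation rule, which Section 7.1 fixes as the next dose. Section 7.1 is the clear prohibition.

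Selection performance moves less than patient numbers. In scenarios 2 and 5 the target-selection gaps are 1.2 and 2.7 points, roughly 0.8 and 1.8 standard errors; scenario 6 moves 5.3 points, in the favourable direction. This is fair.

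The 0.350 explanation of row 3 is an inference from fit, since no text says it was done. I use it only to show that the row does not match its stated inputs.

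The 200% and 250% caps permit the same planned steps (100% and 150%), so that discrepancy is one of wording. A single trial of 9 patients is possible under the plan after a DLE (example 4b); only the mean of 9.2 is impossible.

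**Conclusion.** The concern holds. The stated simulation rule contradicts Section 7.1, Table 10.2:3 does not come from one design, and scenario 4's mean is unattainable under the plan. The scenario 4 result needs only the tabulated rates and the 12-patient path. The row-by-row attribution also assumes the 3 mg reference dose and that the first three columns of Table 10.2:2 are 0.5, 1 and 2.5 mg. Over 2.9 to 3.4 mg the next-dose means barely move (scenario 2: 9.88; 4: 12.02; 5: 11.71–11.72; 6: 12.55–12.68).

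Mean N is wrong by up to 2.8 patients (12.0 against 9.2). Target selection shifts by 0.4 to 5.3 points in scenarios 2, 4, 5 and 6, and by 7.5 in scenario 3, where the rates used are also in doubt. Compared on the same rates, the planned rule selects an overdose less often than skipping does: 12.1% against 21.2% in scenario 3, and 18.3% against 20.2% in scenario 6. The 15-patient maximum and the conservative conclusion therefore survive. The row 5b correction stays below 0.25 and leaves its recommendation unchanged. Nothing here reopens a dose decision. The appendix should be corrected because Section 7.7 relies on it.

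**What to change.** State one escalation rule (next planned dose, one increment cap) and one MFD rule (the current dose, at least 6 patients evaluated, recommended again by the model). Re-run the simulation for the three remaining doses with the Section 7.1 prior and a cap of 15, and with scenarios 1 and 2 set to the current prior medians and means. Replace Tables 10.2:2 and 10.2:3, correct rows 5b and 5c of Table 10.2:1, remove the figures 27.7%, 24, 18 and 500% from the text, and base the Section 7.7 statement on the new output.

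The cost is one re-run of existing R code and an edit of the appendix. Doses, the maximum of 15 patients and the planned analysis do not change.

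### The written MFD rule is met at 12 patients in the appendix's own scenario 5b, where the text doses a third cohort, and Table 10.2:3 does not match that rule either

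*Protocol*

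**What the plan says.** Protocol Section 3.1 (SRD part): "The maximum feasible dose (MFD) is considered as reached if at least 6 patients have been evaluated at a dose level" that the model recommends for the next cohort. Section 10.2, Operating characteristics, repeats this for the simulation: "The MFD was considered reached if at least 6 patients have been evaluated at a dose level", with the same qualifier. Neither place requires the most recent cohort to have been treated at that dose.

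The worked example in Section 10.2 goes differently. At 5b the first dose has 0/6 DLEs and the second 2/6. "If there was no further DLE then (scenario 5b), the recommendation would be to go to next dose", and the dose column of Table 10.2:1 shows this is the second dose. A third cohort is then treated there, and if it has no DLE (5c) "then the trial would stop after 15 patients and declaring" that dose the MFD.

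Table 10.2:3 prints stopped trials of 5.9, 34.6, 62.6, 0, 32.1 and 31.8% for simulation scenarios 1 to 6. Its footnote counts both toxicity stops and trials reaching the patient limit without an MFD. For scenario 1 the text splits the 5.9% into 4.5% for toxicity and 1.4% with no MFD at 15 patients. Section 7.7 rests the figure of about 15 evaluable patients on this simulation.

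**The concern.** Declaring the MFD ends dose finding. If the rule in the design section and the rule behind the worked example differ, the same data lead to two actions: stop at 12 patients, or dose 3 more first. At 5b the difference could matter. The recomputed probability of overdose at the second dose is 0.223, just inside the limit of 0.25. One DLE in a third cohort (3/9) would raise it to 0.309, outside the limit. If the true rate were 0.25, the chance of at least one DLE in three patients is 1 - 0.75^3 = 0.58.

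The operating characteristics, and the 15-patient figure drawn from them, describe the design only if the simulation used the rule that the protocol states.

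**Working it through.** **Step 1: text alone.** In row 5b the recommended dose has 6 patients, 6 >= 6, and the total is 6 + 6 = 12. The written rule is met. Row 5c has 6 + 9 = 15. Rows 4b, 6a, 6d and 6e do not separate the two readings, because there the last cohort was already at the recommended dose.

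**Step 2: rebuild the model.** Inputs are the mixture prior of Table 7.1:1, the doses 0.5, 1 and 2.5 of Table 7.1:2 ("Prior probabilities of DLEs at selected doses"), and the criterion that "there should be less than 25% risk that the true ocular DLE rate is above 0.25". The reference dose d* is redacted. It follows from the stated medians m and prior means (mu1, mu2):

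d* = d * exp(-(logit(m) - mu1)/exp(mu2)).

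For component 1 at the top dose, logit(0.10) = -2.197, (-2.197 + 2.005)/1.053 = -0.182, and d* = 2.5 * exp(0.182) = 3.00. All six stated medians give 3.00.

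Numerical integration then reproduces P(OD) in Table 10.2:1 within about 0.007 (4b 0.088 against 0.091; 6b 0.279 against 0.285; 6d 0.100 against 0.103; 6e 0.098 against 0.098), except for rows 5b and 5c. Row 5b prints 0.022 and 0.116 for the two doses. Recomputed, 5b is 0.059 and 0.223, and 5c is 0.023 and 0.115. The printed 5b values are therefore those of 5c. The second dose passes either way, so the recommendation stands.

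**Step 3: one path by hand.** Follow the recommendations printed in rows 1, 3, 6b and 6c: 0/3 at dose 0.5, 0/3 at 1, 1/3 at 2.5, 0/3 at 1, then 2.5 again. Suppose this fifth cohort has at least one DLE. With 2, 3 or 4 DLEs in 6 at 2.5, P(OD) is 0.346, 0.660 or 0.882, which fails. Dose 1, with 0/6, has 0.017 to 0.080, which passes. At 15 patients the model recommends dose 1, which has 6 patients, so the written rule declares it. If the last cohort must be at the recommended dose, there is no MFD at the limit. With true rates p1, p2, p3 the probability is

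(1-p1)^3 * (1-p2)^6 * 3*p3*(1-p3)^2 * [1-(1-p3)^3].

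- Scenario 6 (0.010, 0.050, 0.400): 0.970 * 0.735 * 0.432 * 0.784 = 24.2%
- Scenario 5 (0.050, 0.010, 0.200): 0.857 * 0.941 * 0.384 * 0.488 = 15.1%
- Scenario 1 (0.014, 0.024, 0.054): 0.959 * 0.864 * 0.145 * 0.153 = 1.8%

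**Step 4: all paths.** Every path of 3-patient cohorts was enumerated exactly, with the first three columns of Table 10.2:2 and a limit of 15. Ranges cover two escalation steps: next planned dose only (Section 7.1), and the simulation's "Escalate to the maximum dose which satisfies the overdose criterion and is" at most a 500% increase.

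| Trials without an MFD (%) | Printed | Written rule | Plus last-cohort condition |
|---|---|---|---|
| Scenario 1, all | 5.9 | 4.2-4.3 | 6.2 |
| Scenario 1, at the limit | 1.4 | 0.0 | 1.9-2.0 |
| Scenario 2 | 34.6 | 26.2-26.9 | 33.4-33.7 |
| Scenario 3 | 62.6 | 48.7-48.8 | 56.6-58.7 |
| Scenario 4 | 0 | 0.3 | 0.4 |
| Scenario 5 | 32.1 | 14.3-15.6 | 29.4-30.9 |
| Scenario 6 | 31.8 | 3.8-4.7 | 28.5-33.6 |

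With 1000 trials the Monte Carlo standard error in scenario 6 is sqrt(0.318 * 0.682/1000) = 1.5 points. The gap under the written rule is at least 31.8 - 4.7 = 27.1 points. Raising the limit to 18 or 24, figures that also appear in Section 10.2, does not close it.

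Under the added condition, 15.1-15.3% of trials in scenario 5 and 24.7-28.9% in scenario 6 meet the written rule yet count as having no MFD.

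**The case against.** **The model only guides.** The SMC decides dose and cohort size, the rule says at least 6, and the SMC may add patients at the final dose. A third cohort at 5b is therefore within its powers. This softens the conflict in conduct. It does not explain the appendix, which presents 5b and 5c as what the model and rule produce.

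**The simulation part is inferred.** The reference dose and the column headings of Table 10.2:2 are redacted, and that table has four columns for three doses. This stands as a limit. Column sets that include the fourth column give 3.8 to 9.1% overdosing MFDs in scenario 5, where the table prints 0, so the first three columns are the better reading of that row.

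**Not every row fits.** With the added condition, scenario 3 gives target/overdosing MFDs of 31.3/12.1% or 20.2/21.2%, depending on the step, against 23.8/13.6% printed. It fits (23.1/14.1%, 62.9% stopped) only if the third rate is 0.35 instead of 0.28. The mean of 11.8 patients in scenario 1 needs the next-dose step (the larger step gives 9.6). The 9.2 in scenario 4 needs the larger step (the smaller gives 12.0). The rows may come from mixed runs, so the added condition is a strong inference for scenarios 2, 5 and 6 and not an established fact about the program.

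**A stronger reading that fails.** A reader might infer that Table 10.2:3 counts many trials with 2 DLEs in 6 as having no MFD. It does not. Most of the trials in question stepped back to a dose with 0/6 DLEs, as in Step 3. Those with at least 2 DLEs at the declared dose are about 0 to 3.5% of trials. The exact 5b path occurs in at most 5.6% of trials with the next-dose step, and essentially never with the larger one.

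**Conclusion.** The contradiction between the written rule and scenarios 5b and 5c can be read off the page and needs no model. That Table 10.2:3 belongs to a different stopping rule is inferred. It rests on d* = 3, the first three rate columns and a limit of 15, but in scenarios 5 and 6 the gap is far beyond simulation error under either escalation step. The 15-patient justification in Section 7.7 therefore cannot be taken as a property of the stated design.

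A reader might also infer that the conducted dose escalation is in doubt. The documents do not support that. Protocol Section 1.2 reports twelve SRD patients and no DLEs, and SAP Section 6.1 gives 12 as the final SRD number. On a path of 12 patients with no DLEs both rules agree. The MD part could start only if the highest dose was tolerated, so an MFD at the second dose would not have led into it. The point is worth correcting for the record; its effect on the trial as run is small.

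**What to change.** - Reconcile Section 3.1 (text and Figure 3.1:1) and Section 10.2 (data scenarios and operating characteristics) to one MFD rule. Which rule applies is for the sponsor and SMC.
- If the written rule is kept, correct the 5b/5c text. If the example's rule is meant, write its condition into both sections and say what follows when 15 patients are reached without an MFD.
- State which stopping rule, escalation step, dose columns and patient limit (24, 15 and 18 all appear) were simulated. Re-run Table 10.2:3 under the chosen rule, or relabel it, and restate the 15-patient sentence in Section 7.7.
- Correct the printed 5b values, which duplicate 5c.

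The cost is protocol wording and a re-run of an existing program. With the SRD part complete, a clarifying note in the trial report would serve the same end.
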